4.2 Secondary objective

- To assess the efficacy of Viscoseal for reduction of post-operative swelling after arthroscopic meniscal repair surgery when compared with standard care.
- To assess the efficacy of Viscoseal for improvement of post-operative patient-reported outcome measures, including pain upon walking and knee functionality, after arthroscopic meniscal repair surgery when compared with standard care.
- To evaluate, as part of a pilot sub-study, if there are any differences in terms of meniscus and knee joint recovery by means of radiological examination using MRI

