5.5 Outcome measures

5.5.1 **Primary outcome measures**

To determine the level of index leg related pain experienced at day 7 post-operation and to compare the average pain scores of patients in the control and Viscoseal arm respectively, through administration of 100 mm visual descriptor scale (VDS) for pain at rest.

The study is powered to detect the established minimal clinically important difference (MCID) of 15 mm on a 100 mm VDS pain.

5.5.2 **Secondary outcome measures**

All the outcome measures are summarised in Table 2.

Table 2. Overview of measurements

Weeks	-12 weeks to day of surgery	48 hours	7 days*	14 days*	12 weeks#	26 weeks~
VDS pain scale for knee (at rest)	Х	Х	Х	Х	Х	Х
VDS pain scale for knee (walking)	Χ				Х	Χ
McGill pain questionnaire (at rest)	Х	X	X	Х		
Limb girth measurement (index leg)	X			Х	Х	
Lysholm scale	Χ				Χ	X
WOMET tool	Χ				Χ	Χ
Use of analgesics / anti- inflammatories	Х	X	Χ	Х	X	X
Patient satisfaction questionnaire re surgery						Χ
MRI scan (sub-study; not all participants)						Х

^{*} Allowed to be up to 2 days early or late

IRAS ref 272362 Page **13** of **30**

[#] Allowed to be up to 2 weeks early or late

[~] Allowed to be up to 4 weeks early or late

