8.3 Secondary outcome statistics

The average baseline demographics for participants in each group will be compared to ascertain that randomisation has indeed led to comparable distribution of participants:

Sex, age, height, weight, BMI, length of stay, type of anaesthetic for surgery and type of analgesics post-surgery.

To compare outcomes between the two groups (standard vs Viscoseal), student t-test, Mann-Whitney U-test or Chi-squared test will be applied as applicable, depending on type and distribution of data .

IRAS ref 272362 Page **19** of **30**

Cox proportional hazards regression analysis will be conducted to investigate the role of Viscoseal and other covariates (as mentioned above) in post-surgery related pain, swelling and knee function.

The statistics apply to:

At least 2 weeks prior to surgery, and 7 days and 14 days post-surgery

- Indication of degree of swelling by measurement of thigh, suprapatellar and calf girth.

Up to 12 weeks prior to surgery, 12 weeks and 26 weeks post-surgery, knee function measurements: Lysholm and WOMET tools.

Descriptive safety overview post-surgery up to 26 weeks:

- Readmitted to theatre and/or hospital
- Infection of wound site
- Diagnosed with pulmonary embolism or deep vein thrombosis.

Patient satisfaction survey at 12 weeks and 26 weeks post-surgery – any difference in outcome will be determined with Mann-Whitney U-test

MRI diagnostics outcomes:

Descriptive statistics, primarily frequencies and averages, to summarise per intervention arm

- Type of injury
- Size of injury
- Grading of injury
- Any recurring or new meniscal injury

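### Section 8.3, read literally, compares limb girth itself between the arms and makes no use of the pre-operative girth that the trial already collects

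*Protocol*

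**What the plan says.** Swelling is the first secondary objective in protocol section 4.2: "To assess the efficacy of Viscoseal for reduction of post-operative swelling after arthroscopic meniscal repair surgery".

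Section 8.3 then fixes four things about its analysis.

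- **Variable:** "Indication of degree of swelling by measurement of thigh, suprapatellar and calf girth".
- **Occasions to which the statistics apply:** "At least 2 weeks prior to surgery, and 7 days and 14 days post-surgery".
- **Between-arm test:** "student t-test, Mann-Whitney U-test or Chi-squared test will be applied as applicable, depending on type and distribution of data".
- **Covariates:** a Cox regression is planned for pain, swelling and knee function, using the covariates named earlier in the section: "Sex, age, height, weight, BMI, length of stay, type of anaesthetic for surgery and type of analgesics post-surgery". Pre-operative girth is not in that list.

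Table 2 in section 5.5.2 schedules girth of the index leg before surgery, at 14 days and at 12 weeks. Appendix 1 has the researcher take the first measurements before surgery. Later forms, with the patient's own measurements, come back by post.

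No sentence says whether the tests are run on girth, on change in girth, or with the pre-operative girth as a covariate.

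**The concern.** Swelling is an increase over a patient's own unswollen girth. Circumference alone mostly reflects build, in a population aged 18 to 59 with BMI up to 35. A knee of 45 cm both before and after surgery has not swollen, yet on girth alone it ranks above one that went from 38 to 41 cm.

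The pre-operative reading would remove most of that irrelevant spread, but section 8.3 gives it no analytic role. It appears only as one more occasion in the list. Section 5.5.3 shows that the protocol can define an outcome relative to baseline: reductions in the meniscal tear are referred to the index tear at baseline. Girth has no such statement.

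At stake is the precision of the swelling comparison. An analysis that follows 8.3 to the letter could miss a real reduction that the collected data could have shown.

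**Working it through.** **The plan's own figure.** There is none for swelling. The sample size in section 6.1 (48 without drop-out, 52 with it, so 24 to 26 per arm) is for 7-day pain. The protocol gives no SD, correlation or effect for girth.

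**Assumed inputs.** Between-patient SD of true girth G = 3 to 5 cm; SD of individual swelling s = 1 cm; measurement error SD at each reading e = 0.7 to 2.0 cm; true reduction d = 1 cm; n = 24 to 26 per arm; two-sided 5%.

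**Formulas.**

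- SD of raw post-operative girth = √(G² + s² + e²)
- SD of change = √(s² + 2e²)
- Residual SD after adjusting for pre-operative girth = √(s² + e² + G²e²/(G² + e²))
- Standard error of the difference = SD × √(2/n); power from the noncentral t distribution

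**One case in full: G = 4, e = 0.7, n = 26.**

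- Raw: √(16 + 1 + 0.49) = 4.18 cm. Standard error 4.18 × √(2/26) = 1.16 cm, so a 1 cm effect is 0.86 standard errors. Power is about 14%.
- Change: √(1 + 0.98) = 1.41 cm. Standard error 0.39 cm, so the effect is 2.56 standard errors. Power is about 71%.
- Adjusted: √(1 + 0.49 + 0.475) = 1.40 cm. Power is about 71%.
- Leg size accounts for 16/17.49 = 91% of the variance of raw girth, and swelling for 1/17.49 = 6%.

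**Across measurement error, G = 4, n = 24 to 26.**

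| Error SD (cm) | Raw girth | Change from pre-operative |
|---|---|---|
| 0.7 | 13–14% | 67–71% |
| 1.0 | 13% | 50–53% |
| 1.5 | 12–13% | 30–33% |
| 2.0 | 12% | 20–22% |

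Baseline-adjusted girth matches change or exceeds it by up to about 2 points. Simulation of 4,000 trials per scenario agrees. With e = 0.7 cm, raw power runs from 10% (G = 5) to 19% (G = 3), while the power of change does not depend on G.

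**A second parametrisation**, by total SD and pre/post correlation ρ, 24 per arm, normal approximation. SD of change = SD × √(2(1 − ρ)); adjusted SD = SD × √(1 − ρ²).

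- SD 4 cm: raw 14%; change 28% (ρ = 0.80), 49% (0.90), 78% (0.95).
- SD 5 cm: raw 10%; change 19% (ρ = 0.80), 34% (0.90), 59% (0.95).

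Change beats raw girth whenever ρ exceeds 0.5. Adjustment helps for any ρ above 0, apart from the trivial loss of one degree of freedom. The direction is the same in every scenario tried; only the size varies.

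**The case against.** **The protocol never says raw girth.** A reader might infer that it defines swelling as absolute circumference and excludes change. It does not. A t-test or Mann-Whitney test can be run on change scores, and the same mixed list of pre- and post-operative times is used for the Lysholm and WOMET scores, so the layout may be only a measurement schedule. This stands. The point is therefore confined to the literal reading and to the absence of any stated use of the pre-operative girth.

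**It could be left to the SAP.** Choosing change or adjustment is often an SAP matter, and an SAP not shown may settle it. However, 8.3 already names the variable, occasions, tests and covariates, and an SAP that followed them faithfully would test unadjusted girth.

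**Randomisation protects the comparison.** A reader might infer bias, or a raised risk that a chance difference in build is taken for an effect. Neither follows: the raw comparison is unbiased on average and chance imbalance is already covered by the 5% level. Only precision is lost.

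**Build is partly adjusted for.** Sex, height, weight and BMI are named for the Cox model of swelling. That is true, but a Cox model does not suit a circumference, which is not a time to an event, and pre-operative girth is still missing.

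**The gain may be smaller.** Patients measure follow-up girth at home, so errors well above 0.7 cm are plausible. This stands, and is why the range runs down to 20 to 23%. The trial is also powered for pain alone and promises no power for swelling.

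**Conclusion.** The point holds as a loss of precision in one secondary outcome. No analysis stated in 8.3 uses the pre-operative girth. Under the assumptions listed, power for a 1 cm reduction is about 10 to 19% on raw girth. On change or adjusted girth it is about 67 to 72%, 50 to 54% or 20 to 23% as measurement error SD rises from 0.7 to 1.0 to 2.0 cm, the last two taken at girth SD 4 cm.

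These figures illustrate and do not predict, because the documents supply no girth SD, error or effect. A reader might take the upper figure as what the trial would achieve; that depends on small measurement error, which home measurement makes uncertain. The direction of the gain does not depend on these choices within the ranges tried. The documents do not support any claim that the swelling comparison is invalid or biased.

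**What to change.** In section 8.3, state that the arms are compared on post-operative girth at each site and scheduled visit by a linear model with arm and pre-operative girth of the index leg as covariate. Report the adjusted difference in cm with its 95% CI. Use the pre-operative value only as a covariate, not as a tested time point. Since the model gives the same treatment estimate whether post-operative girth or change is the response, swelling can still be described as change per arm.

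While editing, reconcile the occasions: 8.3 lists days 7 and 14, but Table 2 schedules day 14 and week 12. The pre-operative window also differs: at least 2 weeks before surgery in 8.3, but from 12 weeks before up to the day of surgery in Table 2.

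The cost is one sentence plus that reconciliation. Pre-operative girth is already collected, so the adjustment needs no new measurement, visit or patient.

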9. DATA HANDLING AND MONITORING

Data arising from this study is confidential. Identifiable information can only be accessed by delegated members of the study team. Anyone in the research team who does not have a substantive contract with North Cumbria Integrated Care NHS Trust or one of the recruiting NHS Trusts will need to apply for a letter of access via the NIHR research passport scheme, should they require access to identifiable study data.

Patient identifiable data will only be used within each respective Trust and by the core research team. All identifiable data is stored on password protected NHS computer systems. Anonymised data will be shared and stored using security-enabled systems such as password-protection and encryption of e-mails and files. The requirements of the Data Protection Act and NHS Code of Confidentiality will be followed at all times. All researchers will be fully trained in NHS Confidentiality and GCP. Participants' GP practices will be informed that they are taking part in the study.

IRAS ref 272362 Page **20** of **30**

All paper data will be held in secure locked environments in the office of the Research & Development department at the Cumberland Infirmary, Carlisle, North Cumbria Integrated Care. Data released (e.g. by publication) will contain no information that could lead to the identification of an individual participant. Upon completion of the study the site files will be archived for a period of 15 years in line with local archiving policy and procedures. Direct access to data only will be granted to authorised representatives from the sponsor / host institution, grant funder and medical device provider (TRB Chemedica UK) and the regulatory authorities to permit trial-related monitoring, audits and inspections.

This investigator-initiated trial will be monitored in terms of conduct of the study by the in-house research team, led by the Chief Investigator, who will convene on a monthly basis in person or via phone/e-mail. A formal trial steering committee will not be convened for this trial — however, when data is available for 50% of the sample an interim analysis will take place to assess if there are any points of concern to consider. The study can be audited by the in-house R&D department as part of their rolling audit programme of sponsored and hosted research studies. As part of the research grant agreement, anonymised study data will be shared with TRB Chemedica UK for review and for potential publication purposes. No identifiable data, including on potential exemplar case photos, will be contained in any of this data.

10. GOVERANCE OF STUDY

10.1 Approvals

This study will be conducted in compliance with the protocol approved by the Health Research Authority, National Research Ethics Service, and local Trust R&D Approval, and according to Good Clinical Practice standards including the Declaration of Helsinki (1964, Amended Oct 2013). No deviation from the protocol will be implemented without the prior review and approval of the aforementioned review bodies, except where it may be necessary to eliminate an immediate hazard to a research subject. In such case, the deviation will be reported according to policies and procedures

10.2 **Sponsor & Indemnity**

North Cumbria Integrated Care NHS Trust is the sponsor of this study and therefore NHS indemnity applies for design, conduct and management of the study. TRB CHEMEDICA (UK) LTD has provided a grant for this study by means of provision of the Viscoseal medical devices and a non-restricted grant worth £6,000.

Patients will not be given financial incentives for taking part in the study. Travel expenses are not offered in this study since patients are not seen in clinic more frequently than they would normally attend as part of their normal care pathway.

11. PUBLICATION AND DATA-SHARING POLICY

The study will be registered on ISRCTN or Clinical Trials Gov website, in line with CONSORT guidelines on good practice in clinical research.

IRAS ref 272362 Page **21** of **30**

The results of this study are planned to be disseminated through:

- Peer-reviewed manuscript in scientific journal
- Internal report to the funder of the trial, TRB CHEMEDICA (UK) LTD

As stated in the PIL and ICF, anonymised study data will be shared with TRB CHEMEDICA (UK) LTD as part of the research grant agreement.

A summary of the main findings can be supplied to participants on request and this will be stated in the informed consent form.

IRAS ref 272362 Page **22** of **30**

APPENDIX 1. TOOLS AND ASSESSMENTS

This appendix contains:

- Visual Descriptor Pain scale
- Short-form McGill pain questionnaire [27]
- Lysholm scale [28]
- Limb girth measurement
- WOMET tool enclosed as a separate document [29]

Visual Descriptor Pain score

[figure not shown]
How painful has your leg, the one has been operated on, been in the last 2 days when resting:

Please put a vertical line on the numbered bar above. We kindly ask you consider the affected knee when you answer this question.

Visual Descriptor Pain score

How painful has your leg, the one has been operated on, been in the last 2 days when walking:

Please put a vertical line on the numbered bar above. We kindly ask you consider the affected knee when you answer this question.

IRAS ref 272362 Page **25** of **30**

Short-form McGill pain questionnaire

PATIENT'S NAME:			DATE:	
	NONE	MILD	MODERATE	SEVERE
THROBBING	0)	1)	2)	3)
SHOOTING	0)	1)	2)	3)
STABBING	0)	1)	2)	3)
SHARP	0)	1)	2)	3)
CRAMPING	0)	1)	2)	3)
GNAWING	0)	1)	2)	3)
HOT/BURNING	0)	1)	2)	3)
ACHING	0)	1)	2)	3)
HEAVY	0)	1)	2)	3)
TENDER	0)	1)	2)	3)
SPLITTING	0)	1)	2)	3)
TIRING/EXHAUSTING	0)	1)	2)	3)
SICKENING	0)	1)	2)	3)
FEARFUL	0)	1)	2)	3)
PUNISHING/CRUEL	0)	1)	2)	3)
VAS PA				WORST POSSIBLE PAIN
PPI				**
0 NO PAIN 1 MILD 2 DISCOMFORTING 3 DISTRESSING	\equiv			
4 HORRIBLE 5 EXCRUCIATING	_			© R. Melzack 198

The short-form McGill Pain Questionnaire (SF-MPQ). Descriptors 1–11 represent the sensory dimension of pain experience and 12-15 represent the affective dimension. Each descriptor is ranked on an intensity scale of 0 = none, 1 = mild, 2 = moderate, 3 = severe. The Present Pain Intensity (PPI) of the standard long-form McGill Pain Questionnaire (LF-MPQ) and the visual analogue scale (VAS) are also included to provide overall intensity scores.

[figure not shown]
The McGill Pain Questionnaire: Major properties and scoring methods . Melzack, 1987

IRAS ref 272362 Page **26** of **30**

Limb girth measurement

There are three places to measure the leg please, see picture below for reference points. Before your surgery, the first measurements will be done by the researcher, so that you can see where exactly the measurements are done. Once done and recorded, please return the completed form with other completed questionnaires to the HIKE study team, using provided FREEPOST envelope (no stamp needed):

- A- Thigh from top of your kneecap, move up 10 cm and then measure around your thigh (ie thigh circumference 10 cm above suprapatellar border)_____(cm)
- B- Top of kneecap with leg stretched, or if not possible in position as in picture below, find top of kneecap and measure knee circumference (ie top of patella, with leg stretched)
 _____(cm)
- **C-** Calf find widest part of calf, usually about 10-15 cm down from kneecap, and measure calf circumference _____ (cm)

IRAS ref 272362 Page **27** of **30**

HIKE protocol v1, dd 1Sep2019

Lysholm questionnaire

Chart 1 - Lysholm Questionnaire (Scale).

Limping (5 points)

Never = 5

Mild or periodically = 3 Strong and continuous = 0

Support (5 points)

No support = 5

Walking stick or crutches = 2

Impossible = 0

Restraining (15 points)

No restraining or restraining feeling = 15 Has the feeling, but no restraining = 10 Occasional restraining = 6 Frequent = 2

Joint restrained at examination = 0

Instability (25 points)

Never miss a step = 25

Seldom, during athletic activities or other strong-effort exercises = 20

Frequently during athletic activities or other strong-effort exercises (or unable to participate) = 15

Occasionally in daily activities = 10

Frequently in daily activities = 5

At each step = 0

Pain (25 points)

No pain = 25

Intermittent or mild during strong-effort exercises = 20 Marked during strong-effort exercises = 15 Marked during or after walking more than 2 Km = 10 Marked during or after walking less than 2 Km = 5 Continuous = 0

Swelling (10 points)

No swelling = 10 Upon strong-effort exercises = 6 Upon usual exercises = 2

Continuous = 0

Climbing stairs (10 points)

No problem = 10 Slightly damaged = 6 One step at a time = 2 Impossible = 0

Squatting (5 points)

[figure not shown]
No problem = 5 Slightly damaged = 4 Not exceeding 90 degrees = 2 Impossible = 0

Total score:

[figure not shown]
Score table: Excellent: 95 - 100; Good: 84 - 94; Fair: 65 - 83; Poor: < 64

All the outcome measures are summarised in Table 2.

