1. LAY SUMMARY

Arthroscopic, or keyhole, surgery of the meniscus in the knee joint has benefits over open surgery. Nonetheless, there is scope to further improve outcomes for patients by reducing pain and discomfort and promoting enhanced recovery of knee joint functionality. The medical device Viscoseal contains hyaluronan and is designed to replenish levels of this compound in the knee joint following arthroscopic repair of the meniscus. Naturally, synovial fluid in the knee joint contains hyaluronan, but a lot of it is washed away when surgeons flush the knee joint during surgery to remove loose pieces of meniscus, cartilage, or bone. Previous studies, both in laboratory studies and patient trials, have demonstrated that Viscoseal can promote re-establishment of biological structure in the knee joint to allow it to return to a normal physiological state and protect cartilage. This present prospective, randomised, controlled trial aims to build on this evidence by comparing standard care versus the injection of Viscoseal (26 vs 26 patients) at the end of arthroscopic meniscus surgery. The degree of pain, leg swelling and knee functionality experienced by patients after surgery will be measured using validated patient surveys focused on the meniscus. The main objective is to determine if Viscoseal can achieve a minimal clinically important difference in pain relief after meniscal repair surgery when compared to standard care.

IRAS ref 272362 Page **7** of **30**

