Patients are in the study for a period of 26 weeks. Thereafter, the patient will be followed up as they would be in normal clinical practice. Two study follow-up visits are aligned to hospital/clinic visits and the other are done remotely. Baseline data can be collected on the day of surgery (prior the actual operation), and 48 hrs, 7 days, 14 days and 12 weeks post-surgery data can be collected when the patient attends for standard follow-up in the orthopaedics out-patient department. The data at week 26 falls outside these dates. In these instances, data can be collected over the phone, via e-mail or by mail (whichever is preferred by the patient – mail is by use of freepost, to avoid patients incurring any costs). The researcher will ask/phone/e-mail/mail the participant at each follow-up time point to check on any adverse event reporting, and if consented by the patient can

IRAS ref 272362 Page **12** of **30**

also send reminders to the participant regarding the completion of certain outcome data at the aforementioned follow-up time points.

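### The Lysholm form in Appendix 1 is unclear in three items worth 30 of 100 points, has one answer that cannot be established remotely at week 26, and leaves a total of 64 in no band

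*Protocol*

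**What the plan says.** The Lay summary says that pain, swelling and knee function will be "measured using validated patient surveys focused on the meniscus". Section 8.3 lists the outcome: "Up to 12 weeks prior to surgery, 12 weeks and 26 weeks post-surgery, knee function measurements: Lysholm and WOMET tools". Table 2 in section 5.5.2 shows the same three time points for both tools.

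Appendix 1 prints the Lysholm form with its points. Three items matter here:

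- *Restraining*, 15 points: "No restraining or restraining feeling = 15 Has the feeling, but no restraining = 10", with further levels at 6 and 2, and a lowest level of "Joint restrained at examination = 0".
- *Climbing stairs*, 10 points: "No problem = 10 Slightly damaged = 6 One step at a time = 2 Impossible = 0".
- *Squatting*, 5 points: "No problem = 5 Slightly damaged = 4 Not exceeding 90 degrees = 2 Impossible = 0".

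The score table below the form ends with "Fair: 65 - 83; Poor: < 64".

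On collection, section 5.4 says that week 12 data can be taken at a standard clinic visit. Week 26 falls outside the clinic dates: "In these instances, data can be collected over the phone, via e-mail or by mail". Section 6.2.1 requires patients to read and write English because surveys are sent electronically. The limb-girth instructions in Appendix 1 ask patients to post that form back together with their other questionnaires.

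**The concern.** The form is fixed in the protocol, so its wording is not something left to a statistical analysis plan. Patients appear to complete it themselves, and in two places the text does not tell them what is being asked. *Restraining* is never defined and is not an obvious name for a knee symptom. *Slightly damaged* describes a thing, not how hard it is to climb stairs or squat. A patient who has to guess, or a member of staff who explains the item over the phone, adds variation that has nothing to do with the knee.

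Separately, one answer presupposes that somebody examines the joint. The protocol assigns nobody to do this at any visit, and it cannot be done by phone, e-mail or mail at week 26.

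At stake is the precision of a secondary outcome in a trial with 26 patients per arm. Section 2 criticises an earlier trial for outcome measures poorly suited to meniscal surgery, so the quality of the instruments is part of this trial's own rationale.

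**Working it through.** All inputs come from the Lysholm form in Appendix 1, with timing from Table 2 and section 8.3 and mode of collection from section 5.4.

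**1. Scale total.** Item maxima in the order printed (limping, support, restraining, instability, pain, swelling, stairs, squatting):

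5 + 5 + 15 + 25 + 25 + 10 + 10 + 5 = 100.

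This reproduces the top of the printed score table, so the scoring arithmetic is intact.

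**2. Share of the scale with unclear wording.** Restraining 15 + stairs 10 + squatting 5 = 30 of 100. The other five items carry 5 + 5 + 25 + 25 + 10 = 70.

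**3. How far one misreading can move a total.**

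| Item | Misreading | Shift in points |
|---|---|---|
| Restraining | item misunderstood altogether (15 against 0) | up to 15 |
| Stairs | 6 taken for a neighbouring answer (10 or 2) | 4 |
| Squatting | 4 taken for a neighbouring answer (5 or 2) | 1 or 2 |

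These are bounds for a single patient. The documents give no misreading rate and no Lysholm standard deviation, so the effect on the group comparison cannot be computed.

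**4. The examination answer.** It scores 0 and the next level up scores 2. If it cannot be established remotely and the patient chooses the next level, the total shifts by 2 − 0 = 2 points. The attainable range becomes 2 to 100 instead of 0 to 100, and only patients at the worst level of that one item are affected.

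**5. The gap at 64.** The bands run 95–100, 84–94, 65–83 and below 64. The items have 3, 3, 5, 6, 6, 4, 4 and 4 answers, so there are 3 × 3 × 5 × 6 × 6 × 4 × 4 × 4 = 103,680 combinations. Enumerating them, 1,597 give a total of 64, and 64 is the only attainable total outside every band. One example in the item order above: 5 + 5 + 10 + 15 + 15 + 6 + 6 + 2 = 64. The share, 1,597 / 103,680 = 1.5%, counts answer patterns. It is not an expected share of patients.

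**6. Use of the bands.** Sections 5.5.2 and 8.3 name the Lysholm scale and define no categorical outcome from it. Section 8.3 lists a Chi-squared test among generic options by data type, without linking it to these classes.

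**The case against.** The strongest case on the other side is that the form still works. The points sum to 100 and every item has ordered answers. *Slightly damaged* sits between *no problem* and a clearly worse level, so its rank can be read from its position. Stairs and squatting have one awkward label out of four each, and a patient at either extreme is unaffected. WOMET measures knee function at the same times. All of this stands, and it limits the point to noise.

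Four stronger readings are tempting, and the documents do not support them.

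- **That the form cannot validly score knee function.** Items worth 70 points are readable, the scoring is coherent, and there is no evidence of actual misreading.
- **That 55 of 100 points are affected.** That count adds the 25-point instability item because its best level speaks of never missing a step. The phrase is ordinary English and the other levels are clear, so 30 is the defensible count.
- **That the scale changes materially between week 12 and week 26.** Section 5.4 allows week 12 data to be collected in clinic but does not say that anyone examines the knee to score this item. The signs of self-completion suggest the same mode throughout. Even if the mode did differ, the effect is at most 2 points.
- **That the form departs from the validated version.** Only the title of reference [28] is available, so this cannot be shown. It can only be checked by the study team.

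**Conclusion.** The point holds as a modest, cheaply corrected defect. Three items worth 30 of 100 points have unclear wording. One answer cannot be established when week 26 is collected remotely, which is worth at most 2 points. A total of 64 has no band, which is an error on the form without consequence for any planned analysis.

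The expected effect is extra measurement noise in one of two knee-function secondary outcomes. Both arms use the same form on the same schedule, so nothing in the documents points to a bias between arms. The primary outcome, pain at rest on day 7, and its sample size are unaffected.

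This rests on two assumptions. Patients complete the form themselves, which the protocol implies (English literacy, electronic surveys, postal return) but does not state for this form. A patient who cannot establish the examination answer picks the next level and does not leave the item blank.

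**What to change.** - Check the Appendix 1 form against the validated English version cited as reference [28], and replace the unclear wording in the restraining, stairs and squatting items.
- Use one self-report form and one scoring rule at baseline, week 12 and week 26, and state the mode of completion, so that no answer depends on an examination that is not done remotely.
- Close the gap so that 64 falls in a band, or drop the bands and analyse the total score only.

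The cost is one replacement form and a minor amendment. Patients already assessed on the present wording need a version flag in the data, so that the analysis can show which form each score came from.
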